3.2.2. If participants withdraw before/during Month 12 due to		
3.2.2.1. Non-COVID-19 related safety reasons (e.g. AE/death, liver chemistry stopping criteria, renal toxicity withdrawal criteria, QTc withdrawal criteria etc., as recorded in eCRF Conclusion form)	No virologic data at Month 12 Window	Disc due to AE/death (Non-COVID-19 related)

Detailed Algorithm Steps		
3.2.2.2. COVID-19 related safety reasons (e.g. AE/death, liver chemistry stopping criteria, renal toxicity withdrawal criteria, QTc withdrawal criteria etc., as recorded in eCRF Conclusion form)	No virologic data at Month 12 Window	Disc due to AE/death (COVID-19 related)
3.2.2.3. Non-safety and Non-COVID-19 related reasons (e.g. Lack of efficacy, protocol deviation, withdrew consent, loss to follow-up, study closed/terminated, investigator discretion etc., as recorded in eCRF Treatment Discontinuation Form)		
○ Last on-treatment VL <50 c/mL OR no on-treatment VL available during study	No virologic Data at Month 12 Window	Disc for other reasons (Non-COVID-19 related)
○ Last on-treatment VL ≥ 50 c/mL AND withdrawal due to Lack of efficacy	HIV-1 RNA ≥ 50	Disc. for lack of efficacy (Non-COVID-19 related)
○ Last on-treatment VL ≥ 50 c/mL AND withdrawal due to all other non-safety related reasons	HIV-1 RNA ≥ 50	Disc. for other reason while not below 50 (Non-COVID-19 related)
3.2.2.4. Non-safety and COVID-19 related reasons (e.g. protocol deviation, withdrew consent, loss to follow-up, study closed/terminated, investigator discretion etc., as recorded in eCRF Conclusion Form)		
○ Last on-treatment VL <50 c/mL OR no on-treatment VL available during study	No virologic Data at Month 12 Window	Disc for other reasons (COVID-19 related)
○ Last on-treatment VL ≥ 50 c/mL AND withdrawal due to Lack of efficacy	HIV-1 RNA ≥ 50	Disc. for lack of efficacy (COVID-19 related)
○ Last on-treatment VL ≥ 50 c/mL AND withdrawal due to all other non-safety related reasons	HIV-1 RNA ≥ 50	Disc. for other reason while not below 50 (COVID-19 related)
a. Excluding permitted change in background therapy where change or decision to change is made prior to/on the first on-treatment viral result		
Examples from FDA guidance		
Data in Window		
Virologic outcome should be determined by the last available measurement while the patient is on treatment and continued on trial within the time window:		

 HIV-1 RNA = 580 c/mL at Day 336, HIV-1 RNA below 50 c/mL on Day 350. This should be categorized as HIV-1 RNA below 50 c/mL. 		
No Data in Window		

Detailed Algorithm Steps

Discontinued study due to Adverse Event or Death:

- Any patient who discontinues because of an AE or death before the window should be classified as *Discontinued due to AE or Death* (as appropriate), regardless of the HIV-1 RNA result, even if the HIV-1 RNA is below 50 c/mL at the time of discontinuation.
- However, if a patient has an HIV-1 RNA value in the time window and also discontinues in the time window, the viral load data should be used to classify the patient's response. This is the Virology First hierarchy:
 - a. HIV-1 RNA below 50 c/mL at Day 336 and discontinues because of AE or even dies on Day 360 — this person is categorized as having HIV-1 RNA below 50 c/mL.
 - b. HIV-1 RNA is 552 c/mL on Day 336 and the patient discontinues on Day 360, the patient is categorized as having HIV-1 RNA \geq 50 c/mL.

Discontinued for Other Reasons:

- Only patients who have achieved virologic suppression can be counted as *Discontinued for Other Reasons*.
- If a patient discontinues the study before the time window because of *lack of efficacy*, then the patient should be included in the HIV-1 RNA \geq 50 row and not in the Discontinued for Other Reasons row.
- If a patient discontinues because *participant withdrew consent* and his or her HIV-1 RNA result at the time of discontinuation was equal to or above 50 c/mL, then he or she should be categorized as HIV-1 RNA \geq 50 and NOT as Discontinued for Other Reasons.
- If a patient discontinued because of *Lost to Follow-Up* and the last HIV-1 RNA result was 49 c/mL, then the patient can be categorized as Discontinued for Other Reasons.
- If patients changed background treatment — *not permitted by protocol*— they should be considered an efficacy failure and captured in the HIV-1 RNA \geq 50 c/mL row.

On study but missing data in window:

- If there are no data during Days 294 to 377, but there is an HIV-1 RNA below 50 c/mL on Day 380, this patient should be considered *On Study but Missing Data in Window*.
- If there are no data during Days 294 to 377, but there is an HIV-1 RNA equal to or above 50 c/mL on Day 280, this patient also should be classified as *On Study but Missing Data in Window*.

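### SAP Appendix 8 contradicts itself on lack-of-efficacy withdrawals whose last on-treatment viral load is below 50 c/mL or absent; the step as written can only lower the HIV-1 RNA ≥50 count

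*SAP*

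**What the plan says.** SAP 13.8 (Appendix 8) sets out the Snapshot algorithm as numbered steps and then reproduces examples from the FDA guidance.

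- **Step 3.2.2.3** applies when there is no on-treatment viral load (VL) in the Month 12 window and the participant withdrew before or during that window. It covers "Non-safety and Non-COVID-19 related reasons (e.g. Lack of efficacy, protocol deviation, withdrew consent" and further reasons of that kind.
- Its first branch is "Last on-treatment VL <50 c/mL OR no on-treatment VL available during study". The outcome is no virologic data at Month 12, with the reason "Disc for other reasons (Non-COVID-19 related".
- Lack of efficacy reaches the HIV-1 RNA ≥50 outcome only through the second branch, "Last on-treatment VL ≥ 50 c/mL AND withdrawal due to Lack of efficacy".
- **Step 3.2.2.4** (non-safety, COVID-19 related) has the same three branches.
- **The FDA example** begins "If a patient discontinues the study before the time window because of" lack of efficacy, and continues "then the patient should be included in the HIV-1 RNA" ≥ "50 row and not in the Discontinued for Other Reasons row". It sets no VL condition.

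Two other sections use the VL-based logic. SAP 7.1.3 ties the ≥50 class for non-AE discontinuations to having a value of at least 50 when treatment stopped. SAP 13.5.3 says that a participant who leaves for a non-AE reason while suppressed is typically counted as having no virologic data, and refers to Appendix 8 for the details. SAP 7.1.1 and 7.1.4.1 name the method as the FDA Snapshot algorithm. SAP 2.1.1, which lists changes from the protocol's planned analysis, mentions only analysis populations.

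**The concern.** The step sends a lack-of-efficacy withdrawal with last VL below 50, or with none, to the very row from which the quoted example excludes it. A programmer following the steps and a reader relying on the example would classify that participant differently, and the SAP does not say which prevails.

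The missing VL condition in the example does not look like loose drafting. The neighbouring examples on withdrawn consent and loss to follow-up both depend on the VL result; the lack-of-efficacy example does not.

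At stake is the proportion with HIV-1 RNA ≥50 c/mL at Month 12, a named secondary endpoint reported with exact confidence intervals. Under the step, a withdrawal recorded as an efficacy failure can be reported as missing data.

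**Working it through.** **Classification.** Take a participant with no on-treatment VL in the window who withdraws before it for a non-safety reason, and set the step beside the quoted examples.

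| Withdrawal reason | Last on-treatment VL | Step 3.2.2.3 | Quoted FDA examples | Agree? |
|---|---|---|---|---|
| Lack of efficacy | <50 | No virologic data | ≥50 | No |
| Lack of efficacy | None | No virologic data | ≥50 | No |
| Lack of efficacy | ≥50 | ≥50 | ≥50 | Yes |
| Other non-safety | <50 | No virologic data | Other reasons (no virologic data) | Yes |
| Other non-safety | None | No virologic data | Other reasons, only if suppression was achieved | Not counted as a conflict: entry requires VL <50 at Screening (Protocol 5.1) |
| Other non-safety | ≥50 | ≥50 | ≥50 | Yes |

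Two of the six cells conflict. In both, the step moves the participant out of the ≥50 row. No cell errs the other way, and none touches the <50 row.

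**Denominators.** SAP 2.4.1 gives 450 evaluable and 474 enrolled patients. These figures are consistent: 450/(1 − 0.05) = 473.7, rounded up to 474; 474/(1 − 0.10) = 526.7, rounded up to the stated 527 screened.

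**Effect per participant.** 1/450 = 0.22 percentage points; 1/474 = 0.21 percentage points.

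**Effect on the reported interval.** SAP 7.1.4.1 specifies Clopper-Pearson limits. For x failures among n, the lower limit is the 2.5% point of Beta(x, n − x + 1), or 0 when x = 0, and the upper limit is the 97.5% point of Beta(x + 1, n − x). The documents give no expected counts, so the counts below are assumptions, with n = 450.

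| Failures under the step | Reclassified under the quoted rule | ≥50 under the step (95% CI) | ≥50 under the quoted rule (95% CI) |
|---|---|---|---|
| 0 | 1 | 0.00% (0.00–0.82) | 0.22% (0.01–1.23) |
| 0 | 3 | 0.00% (0.00–0.82) | 0.67% (0.14–1.94) |
| 5 | 1 | 1.11% (0.36–2.57) | 1.33% (0.49–2.88) |
| 5 | 3 | 1.11% (0.36–2.57) | 1.78% (0.77–3.47) |

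**Can the cells be filled?** Confirmed virologic failure (CVF) needs two consecutive values of at least 200 c/mL (Protocol 7.1.7), so most lack-of-efficacy withdrawals will have a last VL of at least 50. A later on-treatment value below 50 is possible because Protocol 7.1.8.3 lets dosing continue after CVF, at the investigator's discretion, until resistance results arrive. Lack of efficacy with no on-treatment VL at all is improbable.

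**The case against.** The strongest reply is that the step is no isolated slip. SAP 7.1.3 and 13.5.3 carry the same VL-based logic, and 13.5.3 describes a hierarchy that puts virology first, so one illustrative example is the outlier and the step may be a sponsor convention. This stands in part: those sections must change with the step. But neither mentions lack of efficacy, 13.5.3 defers to the appendix, and no departure from the quoted rule is stated or explained.

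The second reply is that the cells will be nearly empty. Protocol 4.3.4 has HAART start as soon as failure is confirmed. SAP Tables 8 and 11 make values after the start of that therapy post-treatment. After Month 2, scheduled HIV-1 RNA falls only at Months 4, 8 and 12, so a further on-treatment value may not be taken. This stands as to frequency, but it does not close the route left by Protocol 7.1.8.3.

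Third, failures stay visible elsewhere: CVF in Tables 2.7 and 2.8, withdrawal reasons in Table 1.4 and Listing 2, and individual Snapshot outcomes in Listing 11. At end of study, Tables 2.3 and 2.4 use observed cases instead of Snapshot. This stands, and it limits the point to the Snapshot outputs of the Month 12 reporting.

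Fourth, step 3.2.2.4 does not list lack of efficacy among its example reasons. Its second branch names it, so the gap is there, but a COVID-19 related case is more remote still.

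A reader might infer that the efficacy results are materially biased. The documents do not support that: the shift is about 0.2 points per case, the endpoint is single-arm and descriptive, and no test or margin depends on it. Nor does the quoted rule settle every case under the step, because it speaks of discontinuation before the window whereas step 3.2.2 also covers withdrawal during it.

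**Conclusion.** The contradiction is real, and the step is wrong by the standard that the appendix itself quotes. Its reach is small. It affects only the split between ≥50 and no virologic data in a secondary descriptive endpoint, by 0.21 to 0.22 percentage points per participant, always towards fewer failures. The likely number of participants is low and could be zero.

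This assumes a denominator between 450 and 474, and that the withdrawal is recorded as lack of efficacy. The second matters because the withdrawal-reason table shell (DISP_T2) also has a separate entry for protocol-defined stopping criteria, and the SAP does not say which a CVF withdrawal would carry.

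**What to change.** - In steps 3.2.2.3 and 3.2.2.4, assign withdrawal for lack of efficacy before the window, with no on-treatment VL in the window, to HIV-1 RNA ≥50 (discontinued for lack of efficacy), whatever the last on-treatment VL.
- Limit the below-50-or-none branch to other non-safety reasons.
- State how a lack-of-efficacy withdrawal during the window, with no VL in it, is classified. The quoted example does not cover that case.
- Amend SAP 7.1.3 and 13.5.3 to match.

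If the sponsor means to keep the VL-based rule, the minimum is to declare the departure from the quoted example and report how many participants it affects.

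The cost is a few text edits and a small change to the Snapshot program. No new data are needed.

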13.9. Appendix 9: Identification of Adverse Events of Special Interest

SMQ and PT codes based on MedDRA dictionary version 23.1 for the Month 12 analysis.

13.9.1. Hepatic Safety Profile

Medical concept of hepatic failure and hepatitis. Sub- SMQs (1) 'Hepatic failure, fibrosis and cirrhosis and other liver damage-related conditions' and (2) 'Hepatitis, non-infectious', both of parent SMQ 'Hepatic Disorders (SMQ code 20000005)'; only narrow terms selected from sub-SMQs. Some preferred terms, e.g. PT 'hepatitis fulminant' are duplicated.

SMQ: 'Hepatic Disorders'; SMQ Code: 20000005	
Sub-SMQ: 'Hepatic failure, fibrosis and cirrhosis and other liver damage-related conditions'	
Category: A	
Scope: Narrow	
Preferred Term	PT Code
Acquired hepatocerebral degeneration	10080860
Acute hepatic failure	10000804
Acute on chronic liver failure	10077305
Acute yellow liver atrophy	10070815
Ascites	10003445
Asterixis	10003547
Bacterascites	10068547
Biliary cirrhosis	10004659
Biliary fibrosis	10004664
Cardiohepatic syndrome	10082480
Cholestatic liver injury	10067969
Chronic hepatic failure	10057573
Coma hepatic	10010075
Cryptogenic cirrhosis	10063075
Diabetic hepatopathy	10071265
Drug-induced liver injury	10072268

SMQ: 'Hepatic Disorders'; SMQ Code: 20000005	
Duodenal varices	10051010
Gallbladder varices	10072319
Gastric variceal injection	10076237
Gastric variceal ligation	10076238
Gastric varices	10051012
Gastric varices haemorrhage	10057572
Gastrooesophageal variceal haemorrhage prophylaxis	10066597
Flood Syndrome	10084797
Hepatectomy	10061997
Hepatic atrophy	10019637
Hepatic calcification	10065274
Hepatic cirrhosis	10019641
Hepatic encephalopathy	10019660
Hepatic encephalopathy prophylaxis	10066599
Hepatic failure	10019663
Hepatic fibrosis	10019668
Hepatic hydrothorax	10067365
Hepatic infiltration eosinophilic	10064668
Hepatic lesion	10061998
Hepatic necrosis	10019692
Hepatic steato-fibrosis	10077215
Hepatic steatosis	10019708
Hepatitis fulminant	10019772
Hepatobiliary disease	10062000
Hepatocellular foamy cell syndrome	10053244
Hepatocellular injury	10019837
Hepatopulmonary syndrome	10052274
Hepatorenal failure	10019845

SMQ: 'Hepatic Disorders'; SMQ Code: 20000005	
Hepatorenal syndrome	10019846
Hepatotoxicity	10019851
Immune-mediated cholangitis	10083406
Immune-mediated hepatic disorder	10083521
Intestinal varices	10071502
Intestinal varices haemorrhage	10078058
Liver dialysis	10076640
Liver disorder	10024670
Liver injury	10067125
Liver operation	10062040
Liver transplant	10024714
Lupoid hepatic cirrhosis	10025129
Minimal hepatic encephalopathy	10076204
Mixed liver injury	10066758
Nodular regenerative hyperplasia	10051081
Nonalcoholic fatty liver disease	10082249
Non-alcoholic steatohepatitis	10053219
Non-cirrhotic portal hypertension	10077259
Oedema due to hepatic disease	10049631
Oesophageal varices haemorrhage	10030210
Peripancreatic varices	10073215
Portal fibrosis	10074726
Portal hypertension	10036200
Portal hypertensive colopathy	10079446
Portal hypertensive enteropathy	10068923
Portal hypertensive gastropathy	10050897
Portal vein cavernous transformation	10073979
Portal vein dilatation	10073209

SMQ: 'Hepatic Disorders'; SMQ Code: 20000005	
Portopulmonary hypertension	10067281
Primary biliary cholangitis	10080429
Regenerative siderotic hepatic nodule	10080679
Renal and liver transplant	10052279
Retrograde portal vein flow	10067338
Reye's syndrome	10039012
Reynold's syndrome	10070953
Splenic varices	10067823
Splenic varices haemorrhage	10068662
Steatohepatitis	10076331
Subacute hepatic failure	10056956
Sugiura procedure	10083010
Varices oesophageal	10056091
Varicose veins of abdominal wall	10072284
White nipple sign	10078438
SMQ: 'Hepatic Disorders'; SMQ Code: 20000005	
Sub-SMQ: 'Hepatitis, non-infectious'	
Category: A	
Scope: Narrow	
Preferred Term	PT Code
Acute graft versus host disease in liver	10066263
Allergic hepatitis	10071198
Alloimmune hepatitis	10080576
Autoimmune hepatitis	10003827
Chronic graft versus host disease in liver	10072160
Chronic hepatitis	10008909
Graft versus host disease in liver	10064676
Hepatitis	10019717
Hepatitis acute	10019727
Hepatitis cholestatic	10019754

SMQ: 'Hepatic Disorders'; SMQ Code: 20000005	
Hepatitis chronic active	10019755
Hepatitis chronic persistent	10019759
Hepatitis fulminant	10019772
Hepatitis toxic	10019795
Immune-mediated hepatitis	10078962
Ischaemic hepatitis	10023025
Lupus hepatitis	10067737
Non-alcoholic steatohepatitis	10053219
Radiation hepatitis	10051015
Steatohepatitis	10076331

13.9.2. Hyperglycaemia

Medical concept of Hyperglycaemia/new onset diabetes mellitus - SMQs (1)

'Hyperglycaemia/new onset diabetes mellitus (SMQ) Narrow SMQ code 20000041.

SMQ: 'Hyperglycaemia/new onset diabetes mellitus '; SMQ Code: 20000041	
Sub-SMQ: 'Hepatic failure, fibrosis and cirrhosis and other liver damage-related	
Category: A	
Scope: Narrow	
Preferred Term	PT Code
Acquired lipotrophic diabetes	10073667
Blood 1,5-anhydroglucitol decreased	10065367
Blood glucose increased	10005557
Diabetes complicating pregnancy	10012596
Diabetes mellitus	10012601
Diabetes mellitus inadequate control	10012607
Diabetes with hyperosmolarity	10012631
Diabetic arteritis	10077357
Diabetic coma	10012650
Diabetic coronary microangiopathy	10080788
Diabetic hepatopathy	10071265

SMQ: 'Hyperglycaemia/new onset diabetes mellitus '; SMQ Code: 20000041	
Diabetic hyperglycaemic coma	10012668
Diabetic hyperosmolar coma	10012669
Diabetic ketoacidosis	10012671
Diabetic ketoacidotic hyperglycaemic coma	10012672
Diabetic ketosis	10012673
Diabetic metabolic decompensation	10074309
Diabetic wound	10081558
Euglycaemic diabetic ketoacidosis	10080061
Fructosamine increased	10017395
Fulminant type 1 diabetes mellitus	10072628
Gestational diabetes	10018209
Glucose tolerance impaired	10018429
Glucose tolerance impaired in pregnancy	10018430
Glucose urine present	10018478
Glycated albumin increased	10082836
Glycosuria	10018473
Glycosuria during pregnancy	10018475
Glycosylated haemoglobin abnormal	10018481
Glycosylated haemoglobin increased	10018484
Hyperglycaemia	10020635
Hyperglycaemic hyperosmolar nonketotic syndrome	10063554
Hyperglycaemic seizure	10071394
Hyperglycaemic unconsciousness	10071286
Impaired fasting glucose	10056997
Insulin resistance	10022489
Insulin resistant diabetes	10022491
Insulin-requiring type 2 diabetes mellitus	10053247
Ketoacidosis	10023379

SMQ: 'Hyperglycaemia/new onset diabetes mellitus '; SMQ Code: 20000041	
Ketonuria	10023388
Ketosis	10023391
Ketosis-prone diabetes mellitus	10023392
Latent autoimmune diabetes in adults	10066389
Monogenic diabetes	10075980
Neonatal diabetes mellitus	10028933
New onset diabetes after transplantation	10082630
Pancreatogenous diabetes	10033660
Steroid diabetes	10081755
Type 1 diabetes mellitus	10067584
Type 2 diabetes mellitus	10067585
Type 3 diabetes mellitus	10072659
Urine ketone body present	10057597

13.9.3. Hypersensitivity Reactions

Notes: Medical concept of hypersensitivity reactions/DRESS. Only narrow terms selected from Category A of SMQ 'Drug reaction with eosinophilia and systemic symptoms syndrome'. Algorithmic approach for this SMQ not used due to complexity in applying and poor specificity of remaining categories. Category A selected as PTs because more specific for concept (only narrow terms) and a pre-requisite for any combination in algorithmic search. Overlap of some preferred terms with SMQ 'Severe Cutaneous Adverse Reactions'. Plus additional preferred terms selected from HGLT 'Allergic conditions' under SOC 'Immune system disorders'.

SMQ: Drug reaction with eosinophilia and systemic symptoms syndrome SMQ Code: 20000225 Category: A Scope: Narrow	
Preferred Term	PT Code
Drug reaction with eosinophilia and systemic symptoms	10073508
Pseudolymphoma	10037127
Additional preferred terms selected from HGLT 'Allergic conditions' under SOC 'Immune system disorders'; HGLT code 10001708	
Preferred Term	PT Code

SMQ: Drug reaction with eosinophilia and systemic symptoms syndrome SMQ Code: 20000225 Category: A Scope: Narrow	
Drug hypersensitivity	10013700
Hypersensitivity	10020751
Type IV Hypersensitivity reaction	10053613
Eosinophillia	10014950
Eye swelling	10015967
Eyelid oedema	10015993
Lip swelling	10024570
Angioedema	10002424
Circumoral oedema	10052250
Face oedema	10016029
Idiopathic angioedema	10073257
Lip oedema	10024558
Mouth swelling	10075203
Oedema mouth	10030110
Periorbital oedema	10034545
Swelling face	10042682
Periorbital swelling	10056647
Swelling of eyelid	10042690
Granulomatous T-cell pseudolymphoma	10084214

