Injection Site Reactions (ISRs)	Clinical experience to date has demonstrated ISRs occur in the majority of exposed participants treated with CAB LA but are generally mild (Grade 1) or moderate (Grade 2) and include events of pain, tenderness, erythema, or nodule formation of several days duration (median duration for individual events <1 week). ISRs may occur more than once in an individual participant receiving multiple injections. Although some Grade 3 ISRs have	Administration advice will be given to minimize risk of poor administration technique giving rise to injection site reactions. Advice on care, monitoring, natural course, and treatment of ISRs is given in study documentation. Advice will be given to participants on care of injection site on day/days immediately post administration, use of analgesia, compresses where appropriate.

Potential Risk of Clinical Significance	Summary of Data/Rationale for Risk	Mitigation Strategy
	been reported, overall ISRs appear tolerable and have not to date been associated with an excess of participants' withdrawal.	Participants will be closely monitored for ISRs particularly for signs of pain, tenderness, infections, erythema, swelling, induration, or nodules (granulomas or cysts) throughout the study.
		Complications of ISRs such as infections (abscess, cellulitis) and collections of fluid requiring drainage will be monitored Significant ISRs may be photographed and referred to a dermatologist for specialist advice.
Hypersensitivity Reactions (HSR)	Hypersensitivity reactions have been reported as uncommon occurrences with integrase inhibitors (INI), including the closely related compound dolutegravir, and were characterized by rash, constitutional findings, and sometimes, organ dysfunction, including liver injury.	The risk of developing a hypersensitivity reaction post administration of IM CAB will be minimized by the use of a 4-week oral lead-in of oral CAB to determine individual safety and tolerability prior to the introduction of IM CAB.
	While there have been no clinical cases of hypersensitivity to CAB to date, there is a theoretical risk of systemic or severe hypersensitivity reactions with or without hepatic symptoms associated with use of IM CAB. The long exposures anticipated	Clinical assessments, laboratory tests (including liver transaminases) and vital signs will be performed throughout this study. Results from these assessments may aid early detection of HSR.

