Hearing Loss ≥ 12 years of age	NA	Hearing aid or intervention not indicated	Hearing aid or intervention indicated	Profound bilateral hearing loss (> 80 dB at 2 kHz and above) OR Non-serviceable hearing (i.e., >50 dB audiogram and <50% speech discrimination)
< 12 years of age (based on a 1, 2, 3, 4, 6 and 8 kHz audiogram)	> 20 dB hearing loss at ≤ 4 kHz	> 20 dB hearing loss at > 4 kHz	> 20 dB hearing loss at ≥ 3 kHz in one ear with additional speech language related services indicated (where available) OR Hearing loss sufficient to indicate therapeutic intervention, including hearing aids	Audiologic indication for cochlear implant and additional speech- language related services indicated (where available)
Tinnitus	Symptoms causing no or minimal interference with usual social & functional activities with intervention not indicated	Symptoms causing greater than minimal interference with usual social & functional activities with intervention indicated	Symptoms causing inability to perform usual social & functional activities	NA
Uveitis	No symptoms AND Detectable on examination	Anterior uveitis with symptoms OR Medical intervention indicated	Posterior or pan- uveitis OR Operative intervention indicated	Disabling visual loss in affected eye(s)
Vertigo	Vertigo causing no or minimal interference with usual social & functional activities	Vertigo causing greater than minimal interference with usual social & functional activities	Vertigo causing inability to perform usual social & functional activities	Disabling vertigo causing inability to perform basic self-care functions
Visual Changes (assessed from baseline)	Visual changes causing no or minimal interference with usual social & functional activities	Visual changes causing greater than minimal interference with usual social & functional activities	Visual changes causing inability to perform usual social & functional activities	Disabling visual loss in affected eye(s)

Systemic

PARAMETER	GRADE 1 MILD	GRADE 2 MODERATE	GRADE 3 SEVERE	GRADE 4 POTENTIALLY LIFE- THREATENING
Acute Allergic Reaction	Localized urticaria (wheals) with no medical intervention indicated	Localized urticaria with intervention indicated OR Mild angioedema with no intervention indicated	Generalized urticaria OR Angioedema with intervention indicated OR Symptoms of mild bronchospasm	Acute anaphylaxis OR Life-threatening bronchospasm OR Laryngeal edema

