Migraine-triggered seizure	10076676
Molybdenum cofactor deficiency	10069687
Multiple subpial transection	10079825
Myoclonic epilepsy	10054859
Myoclonic epilepsy and ragged-red fibres	10069825
Neonatal epileptic seizure	10082068
Neonatal seizure	10082067
Partial seizures	10061334
Partial seizures with secondary generalisation	10056209
Petit mal epilepsy	10034759
Polymicrogyria	10073489
Post stroke epilepsy	10076982
Post stroke seizure	10076981
Postictal headache	10052470
Postictal paralysis	10052469
Postictal psychosis	10070669
Postictal state	10048727
Post-traumatic epilepsy	10036312
Schizencephaly	10073487
Seizure	10039906

SMQ: 'Convulsions' SMQ Code: 20000079 Category: A Scope: Narrow	
Seizure anoxic	10039907
Seizure cluster	10071350
Seizure like phenomena	10071048
Severe myoclonic epilepsy of infancy	10073677
Simple partial seizures	10040703
Status epilepticus	10041962
Sudden unexplained death in epilepsy	10063894
Temporal lobe epilepsy	10043209
Tonic clonic movements	10051171
Tonic convulsion	10043994
Tonic posturing	10075125
Topectomy	10073488
Transient epileptic amnesia	10081728
Tuberous sclerosis complex	10080584
Uncinate fits	10045476
Additional selected preferred terms from HLT Disturbances in consciousness NEC, HLT code 10013509 and HLT Confusion and disorientation, HLT code 10010301.	
Preferred Term	PT Code
Confusional state	10010305
Loss of consciousness	10024855
Syncope	10042772
Sopor	10058709
Stupor	10042264
Altered state of consciousness	10050093
Depressed level of consciousness	10012373
Consciousness fluctuating	10050093

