3.62.	Safety	201584/primary_07/T3.140	Summary of Hypersensitivity Reactions (HSR) Adverse Events of Special Interest by System Organ Class and Preferred Term (Number of Subjects and Occurrences)		M12, EOS
3.63.	Safety	201584/primary_07/T3.143	Summary of Rash Adverse Events of Special Interest by System Organ Class and Preferred Term (Number of Subjects and Occurrences)		M12, EOS

CONFIDENTIAL

213199

Safety: Tables					
3.64.	Safety	201584/primary_07/T3.149	Summary of Bipolar Disorder Adverse Events of Special Interest by System Organ Class and Preferred Term (Number of Subjects and Occurrences)		M12, EOS
3.65.	Safety	201584/primary_07/T3.152	Summary of Psychosis Adverse Events of Special Interest by System Organ Class and Preferred Term (Number of Subjects and Occurrences)		M12, EOS
3.66.	Safety	201584/primary_07/T3.155	Summary of Mood Disorders Adverse Events of Special Interest by System Organ Class and Preferred Term (Number of Subjects and Occurrences)		M12, EOS
3.67.	Safety	201584/primary_07/T3.158	Summary of Sleep Disorders Adverse Events of Special Interest by System Organ Class and Preferred Term (Number of Subjects and Occurrences)		M12, EOS
3.68.	Safety	201584/primary_07/T3.161	Summary of Hyperglycaemia Adverse Events of Special Interest by System Organ Class and Preferred Term (Number of Subjects and Occurrences)		M12, EOS
3.69.	Safety	201584/primary_07/T3.161	Summary of Weight Gain Adverse Events of Special Interest by System Organ Class and Preferred Term (Number of Subjects and Occurrences)		M12, EOS
3.70.	Safety	201584/primary_07/T3.164	Summary of Rhabdomyolysis Adverse Events of Special Interest by System Organ Class and Preferred Term (Number of Subjects and Occurrences)		M12, EOS
3.71.	Safety	201584/primary_07/T3.167	Summary of Pancreatitis Adverse Events of Special Interest by System Organ Class and Preferred Term (Number of Subjects and Occurrences)		M12, EOS
3.72.	Safety	201584/primary_07/T3.170	Summary of Impact on Creatinine Adverse Events of Special Interest by System Organ Class and Preferred Term (Number of Subjects and Occurrences)		M12, EOS

Safety: Tables					
3.73.	Safety	201584/primary_07/T3.173	Summary of Safety in Pregnancy Adverse Events of Special Interest by System Organ Class and Preferred Term (Number of Subjects and Occurrences)		M12, EOS
3.74.	Safety	207966/primary_15/T3.109	Summary of Characteristics of Adverse Events of Special Interest		M12, EOS

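### The hypersensitivity AESI list in SAP 13.9.3 has no preferred term for four of the five events in the protocol's acute allergic reaction grading row

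*SAP*

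**What the plan says.** SAP 13.9.3 gives its scope as "Medical concept of hypersensitivity reactions/DRESS". The list has two parts. For the first, "Only narrow terms selected from Category A of SMQ 'Drug reaction with eosinophilia and systemic symptoms syndrome" are used; that yields two terms, DRESS itself and pseudolymphoma. The second part is described as "Plus additional preferred terms selected from HGLT 'Allergic conditions' under SOC 'Immune system disorders". It holds 19 terms: three hypersensitivity terms, eosinophilia, two angioedema terms, twelve swelling or oedema terms for the face, eyes, lips and mouth, and one further pseudolymphoma term.

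The list feeds Table 3.62, titled "Summary of Hypersensitivity Reactions (HSR) Adverse Events of Special Interest" and broken down by system organ class and preferred term, at Month 12 and end of study. It also feeds the hypersensitivity part of Table 3.74, which characterises adverse events of special interest (AESIs).

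SAP 13.5.4 grades clinical adverse events by the DAIDS table in Protocol Appendix 2. That table's acute allergic reaction row starts at Grade 1 with "Localized urticaria (wheals) with no medical intervention indicated" and reaches "Acute anaphylaxis" at Grade 4. Protocol 2.3.1 says of injectable cabotegravir that "there is a theoretical risk of systemic or severe hypersensitivity reactions", and reports no clinical case with cabotegravir so far.

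SAP 8.3 describes the printed groupings as the current plan. It ties the final terms to what the safety review team has agreed when reporting takes place.

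**The concern.** The list counts swelling of the eyelid or lip as hypersensitivity, but not anaphylaxis. The plan grades events by a table that treats urticaria, bronchospasm, anaphylaxis and laryngeal oedema as forms or degrees of acute allergic reaction. The display meant to report hypersensitivity would nevertheless leave out any of these coded under its own name.

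Hypersensitivity is a named risk of the injectable, and the stated experience so far is no case. An AESI table exists so that a reader need not reassemble a risk from scattered terms. Against that background, even one event left outside the grouping would alter what the hypersensitivity table shows.

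**Working it through.** No sample size, power or error rate is involved, so the check is a comparison of lists.

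**Step 1: size of the lists.** SAP 13.9.3 prints 2 + 19 = 21 preferred terms. SAP 13.9.4 (rash) prints 18 + 20 = 38.

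**Step 2: events in the grading row.** The acute allergic reaction row in Protocol Appendix 2 uses five distinct events: urticaria (Grades 1 to 3), angioedema (Grades 2 and 3), bronchospasm (Grades 3 and 4), anaphylaxis (Grade 4) and laryngeal oedema (Grade 4).

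**Step 3: search both lists by word stem.**

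| Event | Terms in hypersensitivity list (21) | Terms in rash list (38) |
|---|---|---|
| Urticaria | 0 | 0 |
| Angioedema | 2 (Angioedema, Idiopathic angioedema) | 0 |
| Bronchospasm | 0 | 0 |
| Anaphylaxis | 0 | 0 |
| Laryngeal oedema | 0 | 0 |

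So 1 of 5 events has a term of its own and 4 of 5 do not.

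**Step 4: the same result by grade.** Grade 1: 0 of 1 event covered. Grade 2: 1 of 2. Grade 3: 1 of 3. Grade 4: 0 of 3. Coverage is nil at both ends of the scale.

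**Step 5: does SAP 13.9.3 explain the gap?** It gives a reason for not applying the DRESS query's full algorithm: that would be complex to apply, and the remaining categories have poor specificity. This concerns the categories of that query. It does not explain why acute allergic events are absent from the terms added from the allergic-conditions grouping.

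**Step 6: where a missed event would still be shown.** An event coded outside the list remains in Tables 3.10 and 3.11 (all adverse events, Month 12 and end of study). If serious, it is also in Tables 3.27 and 3.30. If it leads to discontinuation, it is in Table 3.32 and Listing 23. Only Table 3.62 and the hypersensitivity part of Table 3.74 would lack it.

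**A separate slip in the same appendix.** In SAP 13.9.14 (seizures), the terms Altered state of consciousness and "Consciousness fluctuating" are both printed with code 10050093. If the search runs on codes, one of the two is not searched for under its own code.

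**The case against.** Four arguments deserve weight.

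*The list is provisional.* SAP 8.3 leaves the final terms to the safety review team. That stands, and it means the gap can be closed without difficulty. It does not put the terms in the plan or oblige anyone to add them.

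*The grading row is a general severity scale, not a definition of this hypersensitivity risk.* Protocol 2.3.1 describes integrase-inhibitor hypersensitivity as rash with constitutional findings and sometimes organ dysfunction. Rash and hepatic events have their own AESI lists, and Protocol 10.6.5.9 manages allergic reactions under a separate heading. This may well explain the emphasis on DRESS, and how wide the concept should be is partly a matter of judgement. But SAP 13.9.3 claims hypersensitivity reactions generally, and it already includes angioedema and facial swelling, which are not part of that description.

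*Some cases would be caught.* An event coded to Hypersensitivity, Drug hypersensitivity, Angioedema or a facial or oral swelling term is counted. This stands. The documents do not allow an estimate of how often coding would go elsewhere.

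*Nothing is lost from the report.* This stands too. Protocol 10.6.5.9 calls for permanent discontinuation after an allergic reaction of Grade 3 or higher judged possibly or probably related, so the severe related cases should be visible in the discontinuation tables.

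A reader might infer that the report would hide an anaphylactic reaction, or that the overall conclusion on hypersensitivity would be too favourable. The documents support neither inference: the event appears in other planned tables, the list may change before reporting, and safety is summarised descriptively with no test or decision attached to Table 3.62.

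**Conclusion.** The omission is real and its effect is confined. Four of the five events in the acute allergic reaction row, including all three at Grade 4, have no term in the hypersensitivity list, and the rash list does not supply one. If the list is used as printed, and an event is coded only to one of those four, Table 3.62 and the hypersensitivity part of Table 3.74 will not count it.

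The number of events affected cannot be calculated, because the documents give no incidence and no coding rules for such events. SAP 13.9.13 is redacted and could not be checked, but 13.9.3 is plainly the hypersensitivity list and Table 3.62 its display.

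The repeated code in the seizure list is a minor, unrelated correction. It matters only if the search is by code, which the SAP does not state.

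**What to change.** Before reporting, and through the safety review team provision in SAP 8.3, add to SAP 13.9.3 the preferred terms for anaphylactic and anaphylactoid reaction and shock, urticaria, laryngeal oedema and bronchospasm. Take them from the MedDRA version in use at that time, so that Tables 3.62 and 3.74 include them.

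The cost is a few entries in a programming list and slightly lower specificity. Urticaria has other causes, and the toxicity table also grades bronchospasm separately as a respiratory event. Because Table 3.62 reports by preferred term, the reader can see what each added term contributes.

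Separately, check the two seizure terms that share code 10050093 in SAP 13.9.14 against the dictionary and correct the one that is wrong.
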